3.1. Exclusions from the Per Protocol Analysis set

A participant meeting any of the following criteria prior to the end of monotherapy period will be excluded from the primary analysis based on the PP analysis set.

Table 2 Criteria leading to exclusion from Per Protocol Analysis set

Number	Exclusion Description
01	Missed at least one dose
02	Took at least one incorrect dose
03	Missed the Day 1 or the Day 11 HIV-1 RNA assessment
04	Missed more than 1 post-Baseline HIV-1 RNA assessment, as per the protocol visit schedule, between Day 1 and Day 10 (inclusive)

Number	Exclusion Description
05	Started the SoC medication prior to Day 11
06	CCI
07	Violated any of the inclusion criteria or met any of the exclusion criteria
08	
Met other Important Protocol Deviations occurring during the monotherapy period meriting exclusion from the PP analysis set as they have the potential to significantly impact primary analysis.
 
 Protocol deviations will be adjudicated throughout the study conduct and will be classified as important (yes/no), along with determination on whether they should trigger exclusion from the PP analysis set and finalised prior to DBL
CCI	

4. STATISTICAL ANALYSES

4.1. General Considerations

4.1.1. General Methodology

If participants prematurely discontinue the study for non-safety reasons prior to Day 11 (primary endpoint), additional replacement participants may be enrolled at the discretion of the sponsor and investigator. These replacement participants will be assigned to the same treatment sequence and same dose as the corresponding participant who prematurely discontinued from the study. Participants will not be replaced if the reason for discontinuation from the study is due to a safety concern, with the exception of SARS-CoV-2 scenarios (see protocol Section 7.2.1).

Data will be summarized by treatment (i.e., VH4004280, VH4011499, placebo matching VH4004280 and placebo matching VH4011499) and dose level, unless otherwise specified.

Data will be summarized either by visit, or separately for the monotherapy period, the Follow-Up period (i.e. AEs only), and/or overall (i.e., monotherapy period plus Follow-Up period), as appropriate for each endpoint, unless otherwise specified. For summaries focusing on the monotherapy period only (i.e. Day 1 – Day 11), if SoC medication for

any participant starts earlier than Day 11 (for any reason), data collected under SoC will be excluded from the monotherapy period (see respective IE in Estimands Section 1.1.1).

Unless, otherwise specified, summary tables will provide the following descriptive statistics:

- Continuous data: n (number of subjects used for data summary), arithmetic mean, standard deviation (SD), median, interquartile range, minimum and maximum. For PK parameters, geometric mean, SD of log-transformed data and geometric %CV_b may also be used. Confidence interval for the mean or geometric mean may also be used (e.g. check mock outputs in OPS).
- Categorical data: number and percentage of participants in each category.

PK values collected outside analysis visit windows will be excluded from data summaries (applies to both Tables and Figures) but will be included in listings. Figures with subject level information will include all values (i.e. irrespective of being within/outside of analysis visit windows). Confidence intervals for PK data summaries will use 95% confidence levels, unless otherwise specified.

Only lab data from central laboratory will be included in lab data summaries. Lab data from local laboratories, if any, will be included in listings (and flagged appropriately).

No imputation for missing values will be performed.

CCI

selected listings required by regulatory agencies will be created in static fashion. See OPS for the list of selected listings.

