4.1. Overall design

This is a Phase 2a, multi-center, randomized, double-blind (sponsor unblinded), placebo-controlled (by each CAI), proof of concept clinical study to evaluate the antiviral effect, safety, tolerability, and PK/pharmacodynamics (PD) of **[REDACTED]** HIV-1 viremic adults.

Up to 42 treatment naïve participants with confirmed HIV-1 RNA \geq 3,000 copies/mL and CD4 T-cell count \geq 200 cells/ μ L will be recruited into this 2-part adaptive study. As per **Figure 1**, the first 14 participants screened and who are found to meet all eligibility criteria will be randomly assigned on Day 1 to one of three placebo-controlled VH4004280 treatment groups (Part 1a: 6 active: 6 active: 2 placebo), followed by the next 14 participants randomly assigned on Day 1 to one of three placebo-controlled VH4011499 treatment groups (Part 1b: 6 active: 6 active: 2 placebo). Each CAI will be evaluated as double-blind monotherapy for 10 days (primary endpoint). On Day 11, after the collection of the HIV-1 RNA sample, participants will start open-label standard-of-care combination antiretroviral therapy that is selected by the investigator and locally sourced. Participants will be followed weekly through Day 39 to ensure that CAI drug concentrations have declined to BLQ.

As described in **9.2**, an informal interim analysis will be conducted after 9 participants (i.e., 4 participants per active arm and 1 placebo participant) from Part 1a have completed their Day 11 visit. A second informal interim analysis will be conducted after 9 participants (i.e., 4 participants per active arm and 1 placebo participant) from Part 1b have completed their Day 11 visit. The conduct of Part 2 is dependent on the results from Part 1 but if conducted, will evaluate a double-blind placebo controlled third pre-specified dose of one or both CAIs in up to an additional 14 participants [(Part 2a: 6 active VH4004280:1 placebo) and/or (Part 2b: 6 active VH4011499:1 placebo)].

Figure 1 Study design schematic

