4.2. Scientific rationale for study design

This is a Phase 2a, multi-center, randomized, double-blind (sponsor unblinded), placebo-controlled, proof of concept clinical study to evaluate the antiviral effect, safety, tolerability, and PK/pharmacodynamics (PD) of orally administered VH4004280 and VH4011499 monotherapy over 10 days in approximately 42 ART naïve HIV-1 viremic adults.

The purpose of this study is to evaluate the short-term safety and effect on reducing HIV-1 RNA levels from baseline for different doses of each orally administered CAI. This study will facilitate an initial understanding of the antiviral activity and safety profile of both CAIs in an HIV positive ARV naïve population, while limiting the monotherapy exposure to reduce the likelihood of development of viral resistance. The data gathered from this study, together with data from the two ongoing Phase 1 studies with CCI [REDACTED] and the single planned Phase 1 study with CCI [REDACTED], will inform subsequent clinical trials and Phase 2b clinical development.

There is an established precedence to use a randomized placebo-controlled short-term monotherapy design in a small number of participants when initially evaluating the activity of new investigational HIV anti-viral agents. This design allows an early understanding of the anti-viral potency and emerging safety profile across different doses of each CAI while limiting the duration of exposure to the fewest number of HIV-infected participants. The placebo control maintains the blind, reduces bias in the investigator's evaluation and management of safety events, and permits a comparison of safety and efficacy outcomes between each CAI and placebo.

The two-part adaptive design will allow for interim evaluation of the exposure-antiviral response data to determine if evaluation of a third dose of one or both CAIs would be informative to properly characterize the exposure-antiviral relationship. If a third dose is not needed, then exposing additional participants to the investigational CAI can be avoided.

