9.4.2.2. Main analytical Approach

The primary efficacy analysis will be based on the Full Analysis Set.

Maximum change from baseline in plasma HIV-1 RNA during monotherapy will be summarized by treatment (i.e., VH4004280, VH4011499, placebo matching VH4004280 and placebo matching VH4011499) and dose level, in original and log10 scales.

In addition, change from Baseline in plasma HIV-1 RNA at each assessment time point during monotherapy will be summarized by treatment and dose level, in original and log10 scales.

Descriptive statistics will be provided as described in Section 9.4.1.

Handling of missing data and Intercurrent Events leading to exclusion of data

Any missing HIV-1 RNA data (e.g., due to missed visits in the clinic, LFU or for any other reason) will not be imputed and will remain missing. Whatever HIV-1 RNA data are available for a participant during monotherapy and prior to starting SOC will be used to calculate maximum VLD.

Participants who withdraw from study prior to the end of monotherapy period, preventing assessment of primary endpoint, no imputation will be performed for missed assessments after their study withdrawal.

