2. STATISTICAL HYPOTHESES

The primary objective will be addressed using an estimation approach (descriptive statistics) with no hypothesis testing. The primary treatment effect to be estimated is the maximum change from Baseline in plasma HIV-1 RNA over the monotherapy period for each dose for both VH4004280 and VH4011499 CAIs.

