4.2.4.1. Summaries of HIV-1 RNA Change from Baseline by Visit

Change from baseline in plasma HIV-1 RNA will be calculated for each participant at each assessment time point during the monotherapy and Follow-Up periods in the original and log10 scales. Change from Baseline at each assessment time point during monotherapy and Follow-Up will be summarized in original and log10 scale using descriptive statistics as described in Section 4.1.1.

Mean and 95% CI of change from baseline in plasma HIV-1 RNA in the log10 scale will be plotted by visit for the monotherapy period.

These analyses will be performed on the FAS, PP analysis set, and Safety analysis set if any participant receives treatment other than the one to which they were randomized.

CCI

CCI

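### Placebo is summarised by default as two groups of 2 or 3; a supplementary pooled placebo group of 4 to 6 would make the HIV-1 RNA reference less imprecise

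*SAP*

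**What the plan says.** SAP 4.1.1 summarises data under four treatment labels and by dose level. Two of the labels are "placebo matching VH4004280 and placebo matching VH4011499". This is a default, which gives way wherever an output specifies otherwise. Protocol 9.4.1 has the same grouping, and protocol 9.4.2.2 applies it to the primary endpoint: "Maximum change from baseline in plasma HIV-1 RNA during monotherapy will be summarized by treatment", with the same two placebo labels.

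Protocol 4.1 fixes the group sizes: "Part 1a: 6 active: 6 active: 2 placebo", "Part 1b: 6 active: 6 active: 2 placebo" and, if Part 2 is opened, "Part 2a: 6 active VH4004280:1 placebo) and/or (Part 2b: 6 active VH4011499:1 placebo".

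Protocol 4.2 gives three reasons for having placebo. Two are protecting the blind and limiting bias in how investigators judge safety events. The third is that the control "permits a comparison of safety and efficacy outcomes between each CAI and placebo".

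The analysis is descriptive. SAP section 2 states: "The primary objective will be addressed using an estimation approach (descriptive statistics) with no hypothesis testing". Intervals are nevertheless planned. SAP 4.2.4.1 says: "Mean and 95% CI of change from baseline in plasma HIV-1 RNA in the log10 scale will be plotted by visit" for the monotherapy period. It does not say which groups the plot shows, so the default grouping applies.

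**The concern.** In a study that estimates and does not test, the value of a control group lies in the precision of what it estimates. An interval for a mean of two people uses a t multiplier on 1 degree of freedom, and it will usually say almost nothing. Yet the study may hold four to six placebo recipients who share one set of eligibility criteria, one HIV-1 RNA assay (protocol 8.2.1) and one visit schedule (protocol 1.3).

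The endpoint makes the placebo reference more important than usual. SAP 4.2.1 defines the primary variable as the change from baseline at each participant's lowest HIV-1 RNA during monotherapy. The lowest of several noisy measurements tends to lie below baseline even if nothing has changed. The active arms cannot separate this offset from drug effect; only placebo recipients can measure it. If it is estimated from two people at a time, the reader cannot tell how much of a modest decline it explains.

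**Working it through.** **Inputs.** Allocation is from protocol 4.1. The SD of maximum decline is redacted in protocol 9.6.1 (Table 8), so results are given in SD units and at assumed SDs of 0.2, 0.3 and 0.5 log10.

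**The plan's own count.** Part 1: 2 × (6 + 6 + 2) = 28. Part 2: 2 × (6 + 1) = 14. The total is 42, which matches the stated maximum. Placebo per compound is 2, or 2 + 1 = 3 with Part 2. Across compounds it is 4 (Part 1 only), 5 (one Part 2 run) or 6 (both), before any replacements.

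**Step 1: interval for a placebo mean.** Half-width = t(0.975, n−1) × SD/√n.

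| n | t | half-width in SD | at SD 0.3 |
|---|---|---|---|
| 2 (split) | 12.706 | 8.98 | 2.70 |
| 3 (split) | 4.303 | 2.48 | 0.75 |
| 4 (pooled) | 3.182 | 1.59 | 0.48 |
| 5 (pooled) | 2.776 | 1.24 | 0.37 |
| 6 (pooled) | 2.571 | 1.05 | 0.31 |

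**Step 2: interval for active minus placebo, one active arm of 6.** With equal variances, half-width = t(0.975, 6+n−2) × SD × √(1/6 + 1/n).

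| placebo n | half-width in SD | SD 0.2 | SD 0.3 | SD 0.5 |
|---|---|---|---|---|
| 2 | 2.447 × 0.816 = 2.00 | 0.40 | 0.60 | 1.00 |
| 3 | 2.365 × 0.707 = 1.67 | 0.33 | 0.50 | 0.84 |
| 4 | 2.306 × 0.645 = 1.49 | 0.30 | 0.45 | 0.74 |
| 6 | 2.228 × 0.577 = 1.29 | 0.26 | 0.39 | 0.64 |

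Gain from pooling: 1 − 1.489/1.998 = 25% (2 to 4) and 1 − 1.286/1.672 = 23% (3 to 6).

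**Step 3: sensitivity to the variance assumption.** With separate (Welch) variances, the simulated median half-width falls from 2.29 to 1.49 SD (35%) or from 1.72 to 1.27 SD (26%). If variance is instead estimated from all arms in use, it falls from 1.80 to 1.34 SD (26%) or from 1.49 to 1.17 SD (21%). The gain is therefore roughly a fifth to a third.

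**Step 4: size of the no-drug offset.** Protocol Tables 1 and 2 give six post-baseline HIV-1 RNA visits through Day 11: Day 2, one on Days 3–5, Days 6 and 7, one on Days 8–10, and Day 11. Assume independent within-person variation and no drug effect. The simulated mean change at nadir is then −0.13 log10 at a within-person SD of 0.1, −0.25 at 0.2 and −0.38 at 0.3. These SDs are assumptions, and correlated errors would change the figures.

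**The case against.** The strongest reply is that the split follows the design. The study is placebo-controlled separately for each compound, and randomisation takes place within sequential blocks. The matched placebo is therefore the only randomised, concurrent control for its compound. Pooling adds people enrolled at another time. It mixes a Day 1 placebo schedule with a Days 1 and 6 schedule (SAP 1.2), and Part 2b may differ again. Protocol 1.3 also allows Part 2 assessment times to be adjusted. All of this stands. It is why pooled placebo should be added beside the matched groups and should not replace them as the reference.

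A reader might infer that the comparison with placebo becomes impossible, or that the placebo interval will overlap any active arm. The documents do not support either reading. The comparison is descriptive, and each compound can be set beside its own placebo. At n=3 and SD 0.3, intervals of ±0.75 and ±0.31 separate once the means differ by more than 1.06 log10. Even at n=2, two values only 0.1 log10 apart give about ±0.64. A reader might also take the fall from 8.98 to 1.59 SD (82%) as the benefit. That figure is for the placebo mean alone; for the comparison the gain is about a quarter.

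For safety the case is weaker. One event reads as 50% of 2 or 25% of 4, but the exact 95% intervals are about 1–99% and 0.6–81%, so pooling cures little.

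The RNA data will all be listed (SAP 4.2.2), so a reader could combine the groups by hand. That would be an unplanned choice made after seeing the data, and it does not put the summary in the plan.

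Finally, the default may be overridden in the OPS or in redacted SAP text. That limit stands.

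**Conclusion.** The point holds as a cheap improvement, not as a flaw that defeats the study. The default placebo groups are 2 or 3 people each, and no readable text plans a pooled summary. The comparison named in protocol 4.2 will be made with little precision. Against one active arm of 6, pooling narrows the 95% half-width from 0.60 to 0.45 log10 (2 to 4 placebo) or from 0.50 to 0.39 (3 to 6), at an assumed SD of 0.3 and equal variances.

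The size of the true effect decides how much this matters. A difference of 1.5 log10 would exceed the split half-width even at SD 0.5 (1.00). A difference of 0.5 log10 at SD 0.3 would fall inside the split half-width at n=2 (0.60) and outside the pooled one (0.45). The gain therefore bears on modest effects and on the nadir offset of roughly 0.1 to 0.4 log10, under the stated assumptions. The conclusion also assumes that placebo recipients in different blocks are similar enough for a descriptive pooled summary, and that no such display is already in the OPS.

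**What to change.** In SAP 4.1.1 and 4.2, define a supplementary *Pooled placebo* group of all placebo participants from every part conducted (n = 4 to 6). Show it in the end-of-study primary and by-visit HIV-1 RNA displays and in the 95% CI plot. Keep the matched-placebo columns in the same displays, labelled as the randomised concurrent reference.

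Optionally add the pooled column to the general AE and liver-panel summaries. Do not add it to AEs leading to discontinuation of study treatment: protocol 9.4.3.1 restricts that table to VH4011499 and its placebo, and pooling would count people who cannot have the event.

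State in a footnote that the pooled group is partly non-concurrent, mixes placebo dosing schedules, and may include Part 2 visits at adjusted times. Record the addition in SAP 4.9. If the OPS already holds such a display, a cross-reference in SAP 4.1.1 is enough.

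The cost is one extra column or line in existing outputs. No participant, visit or dose changes. Protocol section 9 lets the SAP prevail on methods, so a SAP edit before database lock suffices.

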4.1.2. Baseline Definition

For all endpoints, the baseline value will be the latest pre-dose assessment with a non-missing value, including those from unscheduled visits. If time is not collected, Day 1 assessments are assumed to be taken prior to first dose and used as baseline. If Day 1 pre-dose ECG has been assessed more than once (e.g. in triplicate), the average of the available ECG measurements will be used as baseline value.

Unless otherwise stated, if baseline data is missing, no derivation will be performed, and baseline will be set to missing.

Baseline will not be rederived for the Follow-Up period.

4.2. Primary Endpoint(s) Analyses

4.2.1. Definition of endpoint(s)

Plasma HIV-1 RNA values (copies/mL) will be used for the primary efficacy analysis. Change from baseline at the time point where the HIV-1 RNA is minimum (nadir) during the monotherapy period will be calculated for each participant in the original and log10 scales. The change from baseline at nadir is the primary endpoint used to construct the primary estimand (see Section 1.1.1). According to primary estimand definition (Section 1.1.1), if SoC medication starts prior to Day 11 (for any reason), change from baseline values after SoC initiation will be excluded from calculation of change from baseline at nadir.

Note, the change from baseline at nadir during monotherapy is typically the maximum change from baseline in HIV-1 RNA, or in other words the maximum Viral Load Decline (VLD). However, for participants who have all their post-baseline HIV-1 RNA values during monotherapy higher than the baseline value (e.g. as is the potential with some participants randomized to placebo) the change from baseline at nadir is the minimum change from baseline. Also, if a (placebo) participant has a high increase from baseline in HIV-1 RNA and then a smaller decrease from baseline (or vice versa), the maximum change from baseline is at the point where HIV-1 RNA is its peak (zenith); the change from baseline at nadir will be used in this case in the primary analysis. From now on, in this document by “maximum change from baseline in HIV-1 RNA” during monotherapy we will mean the “change in HIV-1 RNA at nadir”.

The log10 transformation is used to allow for comparisons with data publicly available in the same scale from other compounds, and hence aid in interpretation.

4.2.2. Main analytical approach

The primary efficacy analysis will be based on the Full Analysis Set.

Maximum change from baseline in plasma HIV-1 RNA during monotherapy will be summarized in original and log10 scale using descriptive statistics as described in Section 4.1.1.

Any missing HIV-1 RNA data (e.g., due to missed visits in the clinic, LFU or for any other reason) will not be imputed and will remain missing. Whatever HIV-1 RNA data are available for a participant during monotherapy and prior to starting SoC will be used to calculate maximum VLD.

Participants who withdraw from study prior to the end of monotherapy period, preventing assessment of primary endpoint, no imputation will be performed for missed assessments after their study withdrawal.

All HIV-1 RNA data from all participants will be included in a listing.

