7. The assessment of HIV-associated conditions and AEs/SAEs is conducted throughout the study. SAEs are assessed from the time of consent. Non-serious AEs are assessed from the time of first dose. CCI [REDACTED]

Table 2 Schedule of activities – follow-up period with open label standard of care and early discontinuation visit

Clinical Procedures	Follow-Up Phase					Early Discontinuation ⁶
	Visit 8	Visit 9	Visit 10	Visit 11	Visit 12 ⁵	
	Day 11 Fixed visit. No window.	Day 18 +/- 3 day window.	Day 25 +/- 3 day window	Day 32 +/- 3 day window	Day 39 +/- 3 day window	
Outpatient clinic visit	X	X	X	X	X	X
HIV-1 RNA	X Primary endpoint timepoint	X	X	X	X	X
HIV-1 capsid genotype/phenotype	X	X	X	X	X	X
Lymphocyte T-cell subsets (CD4, CD8)	X				X	X
Physical exam ²					X	X
Height, weight, BMI	X				X	X
Vital signs	X	X	X	X	X	X
C-SSRS administration (Since Last Visit form)	X				X	X
12-lead ECG	X	X	X	X	X	X
Safety labs (hematology, chemistry, urinalysis) ³	X	X	X	X	X	X
Serum pregnancy	X	X	X	X	X	X
Plasma PK single sample	X	X	X	X	X	X
Plasma for storage	X	X	X	X	X	X
AE/SAE assessment	X	X	X	X	X	X
HIV-associated conditions	X	X	X	X	X	X
Concomitant medication review	X	X	X	X	X	X
Standard of care cART ¹	X	X	X	X	X	X

1. Standard of care cART will be chosen by the investigator and first dose will be directly observed at the end of the Day 11 visit. Choice of cART will be informed by local treatment guidelines, accessibility and locally run genotypic/phenotypic results (if available).
2. Complete Physical Exam performed at Screening and Day 39/Early Discontinuation. A symptom directed physical exam will be performed at all other noted visits. Any abnormalities to be recorded as AEs.
3. See Section 10.2 for details of clinical laboratory tests. Fasting bloodwork for the lipid panel is required at Days 1, 6, 11, 25, 39/Early Discontinuation.

CONFIDENTIAL

218307
Protocol Final

4. Plasma samples for storage will be collected at each visit, including unscheduled visits. These samples will be used when needed, such as when samples are lost or where quantity is insufficient for testing. In the event samples are not used by study completion and consent is obtained for further research, then the stored samples may be utilized for additional research on antiretroviral resistance and/or HIV-1 disease biology/host immune response (excluding any human genetic testing).

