4.3. Justification for dose

The VH4004280 and VH4011499 doses for investigation in this study are defined by emerging PK and safety data from the ongoing oral Phase 1 studies, preclinical potency data [RPS-CLIN-048482; RPS-CLIN-026329; RPS-CLIN-047476; RPS-CLIN-046304; RPS-CLIN-056829; RPS-CLIN-056826; TMF-14580566; TMF-14086139; TMF-14580566], and CCI [REDACTED]

A therapeutic dose for VH4004280 and VH4011499 is proposed where majority of participants maintain, concentrations CCI [REDACTED]

[REDACTED], that are expected to provide exposures that result in a near maximal change from baseline in plasma HIV-1 RNA by Day 11.

Thus, VH4004280 and VH4011499 doses in the current study aim to provide the following exposures through the 10-days monotherapy period:

- CCI [REDACTED] aimed to characterize the near maximal decline in HIV-1 RNA.
- CCI [REDACTED] aimed to characterize the near maximal decline in HIV-1 RNA.
- Based on the interim analysis of exposures and response, a dose corresponding to 10-days CCI [REDACTED] [REDACTED] aimed to confirm the maximal decline in HIV-1 RNA.

A population pharmacokinetic (POP PK) analysis was conducted using preliminary data from the ongoing oral Phase 1 studies for VH4004280 and VH4011499 [TMF-15100069; TMF-14909676]. Based on the POP PK analysis, CCI [REDACTED]

[REDACTED] Similarly, using a POP PK analysis for VH4011499, CCI [REDACTED]

Thus, VH4004280 doses for the current study are expected to be CCI [REDACTED]

[REDACTED] for Part 1 and a dose between approximately CCI [REDACTED]

[REDACTED] will be selected for Part 2 based on interim analysis. Similarly, VH4011499 doses for the current study are expected

to be CCI

for Part 1 and a dose between approximately CCI

will be selected for Part 2 based on interim analysis. VH4004280 and VH4011499 doses in Part 2 may be adjusted based on preliminary analyses of exposure and response from Part 1.

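### Does a nadir endpoint that averages below zero without drug need a supplementary Day 11 active-minus-placebo difference?

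*SAP*

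**What the plan says.** SAP 2 sets an estimation approach without hypothesis tests and states: "The primary treatment effect to be estimated is the maximum change from Baseline in plasma HIV-1 RNA over the monotherapy period for each dose". SAP 4.2.1 fixes the meaning of maximum change: "The change from baseline at nadir is the primary endpoint used to construct the primary estimand". It also discusses placebo participants whose values all rise, or whose rise exceeds their fall. SAP 4.2.2 then says: "Maximum change from baseline in plasma HIV-1 RNA during monotherapy will be summarized in original and log10 scale using descriptive statistics". The layout comes from SAP 4.1.1: "Data will be summarized by treatment (i.e., VH4004280, VH4011499, placebo matching VH4004280 and placebo matching VH4011499) and dose level". Each compound's placebo is therefore a separate group, and the same section allows a confidence interval for the mean.

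SAP 4.2.4.1 adds the change from baseline at each visit, on the original and log10 scales, for the FAS and the PP set (and the Safety set if anyone receives a treatment other than the randomised one). It also adds a plot by visit of the log10 mean with its 95% CI over the monotherapy period. SAP 6.2.2 places Day 11 assessments other than AEs in that period when times are not collected.

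Protocol 4.2 says the placebo control "permits a comparison of safety and efficacy outcomes between each CAI and placebo". Protocol Table 2 labels the Day 11 HIV-1 RNA sample "Primary endpoint timepoint". Protocol 4.3 describes exposures "aimed to characterize the near maximal decline in HIV-1 RNA".

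**The concern.** A minimum taken over several noisy measurements is biased downwards as a measure of change. An inert dose would show an average fall, and most untreated participants would appear to have responded. Because SAP 2 calls this quantity, dose by dose, the primary treatment effect, a reader could take an arm mean of a few tenths of a log as drug activity.

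The usual safeguard is the placebo group, and Protocol 4.2 says it is there for comparison. Yet no readable passage of the SAP specifies an active-minus-placebo difference or an interval for one. A weakly active dose is where this could mislead, and SAP 4.7 allows Part 2 to test a lower dose than those in Part 1. The natural suggestion is a supplementary difference in log10 change at Day 11, active minus own-compound placebo, with a 95% CI.

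**Working it through.** **Inputs from the documents.** There are six scheduled post-baseline HIV-1 RNA samples in monotherapy: Days 2, 3-5, 6, 7, 8-10 and 11 (Protocol Tables 1 and 2). Each compound has 6:6:2 participants in Part 1 and 6:1 in Part 2 (Protocol 4.1). The stated total reproduces: 2 × 14 + 2 × 7 = 42. There is no power figure to reproduce, and the precision table (Protocol Table 8) is redacted.

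**Assumption.** The within-person SD of one log10 value, s, is not readable. I use 0.10 to 0.30, with normal and, unless stated, independent errors. Simulations use 400,000 participants with visits at Days 1, 2, 4, 6, 7, 9 and 11.

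**Step 1: the offset with no drug effect.** The expected minimum of six independent standard normal values is -1.267, so the mean nadir change is -1.267 × s.

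| s | Independent errors | Equal correlation 0.5 |
|---|---|---|
| 0.10 | -0.13 | -0.09 |
| 0.20 | -0.25 | -0.18 |
| 0.30 | -0.38 | -0.27 |

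About 6/7 = 86% of untreated participants would show a fall. The offset is real.

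**Step 2: the excess when the drug works.** This is the nadir mean beyond the true Day 11 change, at s = 0.20 and 0.30.

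| True Day 11 fall | Linear to Day 11 | Plateau from Day 7 |
|---|---|---|
| 0.5 log | 0.10 to 0.21 | 0.19 to 0.31 |
| 2 log | 0.01 to 0.04 | 0.17 to 0.26 |

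**Step 3: which move removes it.** The change at a fixed day involves no selection, so the mean Day 11 change equals the true Day 11 change in every scenario. That holds for each arm alone, before any placebo value is subtracted. The by-arm Day 11 summary is already in SAP 4.2.4.1.

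**Step 4: what subtraction costs.** With independent errors, the SD of the Day 11 change is √2 × s = 0.283 at s = 0.20. Standard errors:
- Planned Day 11 arm mean, n = 6: 0.283/√6 = 0.12.
- Day 11 difference, 6 v 2: 0.283 × √(1/6 + 1/2) = 0.23.
- Day 11 difference, 6 v 3: 0.283 × √(1/6 + 1/3) = 0.20.

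All three are unbiased here, so these are also their root mean square errors (RMSE). For the nadir arm mean, RMSE against the Day 11 effect is √(bias² + variance/6):
- 0.5 log, linear: √(0.104² + 0.248²/6) = 0.15.
- 0.5 log, plateau: √(0.193² + 0.244²/6) = 0.22.
- No effect: √(0.253² + 0.238²/6) = 0.27.

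At 6 v 2, the difference therefore beats the nadir mean only when there is no drug effect. At 6 v 3, it also does slightly better under the plateau (0.20 against 0.22). It never beats the planned Day 11 arm mean. At s = 0.30 the 6 v 2 pattern is the same: planned Day 11 mean 0.17; nadir mean 0.26 (linear) and 0.34 (plateau); difference 0.35.

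**Step 5: the interval.** For a common-variance model across one compound's arms, the half-width is t × √(1/n1 + 1/n2) × SD.
- Part 1 (14 participants, 3 arms, 11 df): 2.201 × 0.816 = 1.80 SD, or 1.80 × 0.283 = 0.51 log10.
- With Part 2 (21 participants, 4 arms, 17 df): 2.110 × 0.707 = 1.49 SD, or 0.42 log10.
- Planned one-arm Day 11 interval (5 df): 2.571/√6 = 1.05 SD, or 0.30 log10.

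The offset to be corrected is 0.25 log10. With separate variances, the difference has a median half-width of about 2.3 SD (6 v 2) or 1.7 SD (6 v 3).

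**The case for a change.** The best case for the addition is that it is cheap and uses the placebo group for its stated purpose. A reader who subtracts one row from another gets no interval, and a placebo mean on its own has a 95% half-width of 8.98 SD (n = 2) or 2.48 SD (n = 3). A common-variance model brings the difference down to 1.80 or 1.49 SD and shows its uncertainty openly. There is also a real risk of misreading: at s = 0.20, a 95% interval around the nadir mean of six untreated participants would lie wholly below zero in about 46% to 55% of arms, depending on autocorrelation, against about 2.5% for the Day 11 change. SAP 4.2.1 comments on odd placebo patterns but does not mention the offset.

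These facts stand. They support reading the nadir table beside the Day 11 summary, which the plan already supplies. They do not show that the plan estimates the wrong thing: its summary measure is the mean maximum change, and the arm mean estimates it. A Day 11 difference is a different quantity. It leaves the offset in the primary table and misses an earlier nadir if virus rebounds. Subtraction would protect against a systematic drift in untreated viral load, but two or three placebo participants give little protection. The narrower interval also depends on a common variance that so few placebo participants cannot check.

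**Conclusion.** No change is needed. The nadir mean is below zero without drug, by about 1.27 within-person SDs under independent errors and less under correlation. A fixed-day summary that avoids this is already planned by arm, placebo included, with 95% CIs plotted by visit. The suggested contrast would double the error of that summary in Part 1 and have a half-width of about 0.51 log10 at s = 0.20, too wide to settle an effect of 0.5 log or less. For a 2-log fall, the excess at s = 0.20 to 0.30 is 0.01 to 0.04 log10 if the decline is linear and 0.17 to 0.26 if it plateaus from Day 7. Neither would put in doubt that the drug is active.

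The study is sized on feasibility and reports estimates without tests, and no readable decision rule uses a placebo-subtracted value. Presenting such a difference is a matter of taste for the study report. An analyst can note the offset there and point to the Day 11 rows without amending the SAP.

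The log10 sizes depend on the assumed SD and on normal errors. The statement that no contrast is specified covers readable text only: parts of the SAP after 4.2.4.1 are redacted, and the OPS and the separate CPMS report are not available. A contrast found there would only strengthen the conclusion.
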